4.3 Subject Recruitment, Enrollment and Screening

For recruitment into the study, we will recruit patients from our Mayo Clinic Gynecology clinics, but we will look to our colleagues for referrals for the study. Before the start of the study, a letter will be sent to all staff providers in Gynecology (n = 69) and Family Medicine at Mayo Clinic (n = 166) and primary care providers at affiliated facilities (n= 81), including the Mayo Clinic Health System sites, for referrals to our gynecology clinics for the trial. The trial will be listed under our current studies section and at clinicaltrials.gov. The advertising brochure will be downloadable as a PDF file and flyers created for display in our medical facilities.

Self-referrals to our clinic for evaluation of the study will be allowed. We will use our Mayo Clinic Fibroids social media network (Facebook and Twitter) developed for our current fibroid studies and the assistance of our Mayo Clinic Division of Community Engagement for outreach. We have established an email address for fibroid studies that will be listed on brochures and flyers. Based on an accrual feasibility study, we project that we can recruit all of our patients from Mayo Clinic Rochester alone. We can reach out to 3 of our Mayo Clinic Health System hubs for additional referrals and outreach if needed as we are currently doing with other trials. In addition, all women seeking treatment for HMB will be advised of the study when making their appointment. They will be offered a brochure, and the option to talk with a study coordinator during their clinical visit. We estimate that we will enroll a minimum of 3 participants per week (13 months to reach target enrollment of 160 participants).

Informed consent for study enrollment will be obtained by a study coordinator in the clinic setting. The consent document and study treatments will be reviewed with the patient, and she will be allowed sufficient time to ask questions.

4.4 Early Withdrawal of Subjects

4.4.1 When and How to Withdraw Subjects

Participants may be withdrawn from the study at any time prior to completion of the study for the following reasons:

- Safety issues including allergic or adverse reaction to either medication
- If the participant develops clinically significant anemia from on-going HMB, she will be offered different treatment options
- Displacement of LNG-IUS will require removal and participant may opt to withdraw from study or have a new device placed
- Participant decision to withdraw from study (withdrawal of consent)
- Unable to comply with the study protocol

There are no adverse effects from stopping either treatment suddenly. We will encourage the participant to complete the study end measures (clinical laboratories, ultrasound, exam) to provide useful information to provide their primary care or gynecological provider on the management of their HMB. This data will be useful to understand the treatment effect on the fibroids, bleeding, and well-being of the participants. If withdrawn from the study and not agreeable to the additional measures, we will use only data collected to that point. We will plan our recruitment to account for 20% attrition from the study so that individual participants will not require replacement.

4.4.2 Data Collection and Follow-up for Withdrawn Subjects

We will use the data obtained up until the person withdraws from the study, but will attempt to obtain permission for follow-up at 9 months for the subjects who have withdrawn. This endpoint will include whether the participant is still using either of the treatments, has any adverse events from treatment, had other procedures for HMB, and if there was expulsion of intrauterine device.

[figure not shown]
5 Study Drug

5.1 Description

[figure not shown]
Neither arm will be blinded due to the nature of the therapy.

Mirena (levonorgestrel-releasing intrauterine system) contains 52 mg of LNG, a progestin, and is intended to provide an initial release rate of approximately 20 mcg/day of LNG.

Levonorgestrel USP, (-)-13-Ethyl-17-hydroxy-18,19-dinor-17 α -pregn-4-en-20-yn-3-one, the active ingredient in Mirena, has a molecular weight of 312.4, a molecular formula of C₂₁H₂₈O₂, and the following structural formula:

LYSTEDA is an antifibrinolytic drug. The chemical name is trans-4-aminomethylcyclohexanecarboxylic acid. The structural formula is:

Tranexamic acid is a white crystalline powder. It is freely soluble in water and in glacial acetic acid and is very slightly soluble in ethanol and practically insoluble in ether. The molecular formula is C₈H₁₅N₀₂ and the molecular weight is 157.2.

Tranexamic acid tablets are provided as white oval-shaped tablets and are not scored. Each tablet is debossed with the marking "FP650." The active ingredient in each tablet is 650 mg tranexamic acid. The inactive ingredients contained in each tablet are: microcrystalline cellulose, colloidal

silicon dioxide, pregelatinized corn starch, povidone, hypromellose, stearic acid, and magnesium stearate.

5.2 Treatment Regimen

LNG-IUS is effective on placement and can be used up to 5 years. TXA will be dosed at 1300mg (2 tablets of 650mg) three times a day at the start of menses and used during the days that bleeding is heaviest (not to exceed 5 days per menstrual cycle).

5.3 Method for Assigning Subjects to Treatment Groups

After review of enrollment criteria, eligible participants will be randomly assigned to either LNG-IUS or TXA treatment. Using a computer generated random numbers sequence; our statistician will prepare the randomization code. Randomization will be stratified by BMI (≥ 30 or < 30), dysmenorrhea (yes/no) and duration of HMB (< 1 or ≥ 1 year) and will be conducted using a dynamic allocation approach based on the Pocock-Simon method.

For patients that decline randomization but meet criteria and are interested in participation, they will be followed in the treatment group that they choose (either the LNG-IUS or TXA options).

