1.4 Dose Rationale and Risk/Benefits

Both medications are being used at the clinically acceptable dosages as indicated for the treatment of HMB. Risks of LNG-IUS related to fibroids include expulsion, perforation, or embedment of device. The risk of TXA related to fibroids is necrosis of the fibroids leading to pain.

2 Study Objectives

Primary Objective

To determine the comparative effectiveness [as measured by the Menorrhagia Multi-Attribute Scale (MMAS)] and duration of use of TXA versus LNG-IUS for the treatment of HMB in women with uterine fibroids.

Hypothesis: A user-independent medical therapy (LNG-IUS) will result in better patient reported outcomes and longer use compared to self-administered medication (TXA)

Secondary Objective

To determine the clinical and fibroid-related predictors of successful medical therapy of HMB in women with uterine fibroids.

Hypotheses: Large fibroid size will limit the effectiveness of LNG-IUS compared with TXA; elevated BMI predicts higher success with LNG-IUS over TXA.

[figure not shown]
3 Study Design

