7.1 Sample Size Determination

Aim 1. The primary outcome variable will be the difference in MMAS score at 6 months between the treatment arms. Based on the ECCLIPSE trial, the observed effect size at 6 months for the MMAS total score was 0.58 standard deviations (8). In order for the proposed trial to

have 90% power to detect such a difference, we would need 64 patients per treatment arm. To allow for up to 20% loss to follow-up or incomplete data without the potential to carry-forward an MMAS score from an earlier assessment, we will enroll 80 patients per treatment arm. From our preliminary study of a large insurance-claims database, we found a 40% difference (62% vs. 22%) in continued use of the index medication at 6 months. Based on the sample size of 80 women per arm, we will have over 90% power to detect such a difference if it exists in the data from the proposed trial. These calculations are based on a two-sample t-test and chi-square test, respectively, assuming a type I error of 0.05 and a two-sided alternative hypothesis.

Aim 2. As described in Aim 1, we plan to enroll 80 patients in each treatment arm. Among these 160 patients, we anticipate that at least 80 patients will have intentionally discontinued treatment by the end of the study. Table 3 below summarizes the detectable hazard ratios for different factor scenarios with varying prevalence. Assuming that 50% of the study participants will have a BMI > 30 kg/m², this aim will have 80% power to detect an association between obesity and intentional discontinuation.

Table 2. Detectable hazard ratios with 80% power based on a two-sided logrank test with a type I error of 0.05	
Prevalence of factor	Among the 160 patients in both arms (assume 80 intentionally discontinue)
20%	2.19
30%	1.98
40%	1.90
50%	1.88

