7.2 Statistical Methods

Descriptive Statistics

Standard descriptive statistics will be generated for measurements at baseline, 3, 6, and 9 months, including mean, median, standard deviation (SD), and interquartile range (IQR) for continuous variables and counts and percentages for categorical variables.

Handling of Missing Data

Last value carry forward (LVCF) methods will be investigated to accommodate drop-outs.

Primary Hypothesis: A user-independent medical therapy (LNG-IUS) will result in better patient reported outcomes and longer use compared to self-administered medication (TXA)

Statistical analysis: The distribution of each of the continuously scaled outcome measures (MMAS total score, PBLAC score, ferritin level, hemoglobin level, UFS-QOL scores, and Rand

SF-36 composite scores) will be graphically evaluated and logarithmic transformations will be applied if the distributions are skewed in order to obtain more normally distributed distributions. At 3, 6, and 9 months separately, each of the continuously scaled outcomes will be compared between treatment arms based on fitting separate linear regression models. In addition, separate analysis of covariance (ANOCOVA) models will be fit to compare the measures between the two treatment arms after adjusting for baseline levels. The cumulative incidence (CI) function will be used to estimate the cumulative proportion of patients by time t who have intentionally discontinued treatment due to the desire or need to stop or switch treatment, after accounting for the competing risk of LNG-IUS expulsion and censoring all other participants at their date of last follow-up or end of study. Likewise we will also estimate the CI of expulsion among the LNG-IUS treatment arm. The CI estimates for intentional discontinuation over the entire 9 months of follow-up will be compared between treatment arms using the methods developed by Gray (34). All analyses will be performed based on the intention to treat principle and calculated p-values will be based on two-sided hypothesis tests. P-values less than 0.05 will be considered statistically significant. Statistical analyses will be performed using the SAS version 9.4 software package and packages in R (Version 3.1.1).

Secondary Hypothesis 1: Large fibroid size will limit the effectiveness of LNG-IUS compared with TXA; elevated BMI predicts higher success with LNG-IUS over TXA.

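### Baseline fibroid size, a predicted effect modifier, is missing from the MMAS models; adding it is a free gain in precision, not the repair of a bias

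*Combined protocol and SAP*

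**What the plan says.** **Prediction.** The secondary hypotheses in Section 2, repeated in 7.2, read: "Large fibroid size will limit the effectiveness of LNG-IUS compared with TXA; elevated BMI predicts higher success with LNG-IUS over TXA". Size and BMI stand side by side, with no ranking.

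**Allocation.** Section 5.3 states "Randomization will be stratified by BMI", then adds "dysmenorrhea (yes/no) and duration of HMB". Assignment "will be conducted using a dynamic allocation approach based on the Pocock-Simon method". BMI is therefore balanced; fibroid size, number and location are not.

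**Primary MMAS analysis.** Section 7.1 states: "The primary outcome variable will be the difference in MMAS score at 6 months between the treatment arms". Section 7.2 gives two analyses. In one, "each of the continuously scaled outcomes will be compared between treatment arms based on fitting separate linear regression models", with no covariate named. The other is an ANCOVA to "compare the measures between the two treatment arms after adjusting for baseline levels". The plan does not say which is primary, and size is in neither.

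**Where size is analysed.** Under the secondary hypothesis, 7.2 puts covariates into Fine-Gray models of intentional discontinuation and of expulsion, and explores whether the factors differ by arm. No MMAS model has a size term or a size-by-arm term.

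**Availability.** Section 3.1 has number and size of fibroids documented by ultrasound at screening, and 4.1 requires image-confirmed fibroids of at least 1 cm. A baseline value should therefore exist before randomisation.

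**The concern.** The trial is meant to cover a range of fibroid sizes. Section 4.2 caps uterine size and sounding length but not the fibroid itself, so size may vary widely. The protocol expects this variable to change how the two treatments compare. It balances the other predicted modifier and gives no reason for leaving size out.

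If size is also related to 6-month MMAS, leaving it out of the model leaves its variance in the residual, and any chance difference in size between arms stays unadjusted. The predicted modification is also never examined on the MMAS, although the hypothesis concerns effectiveness and Section 2 measures effectiveness by that score.

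**Working it through.** **1. The plan's own figures.** Inputs from 7.1: effect 0.58 SD, 90% power, two-sided 0.05, two-sample t-test. The t-test calculation gives 63.4, rounded up to 64 per arm, with power 90.2% at 64. Allowing for 20% loss, 64 / 0.80 = 80 per arm. Both figures reproduce.

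**2. Chance imbalance.** The documents give no prevalence of large fibroids, so I assume 20% to 50%. The SD of the between-arm difference in prevalence is sqrt(2p(1−p)/n), treating allocation as simple randomisation with respect to size.

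| n per arm | p | SD | 95% limit (1.96 × SD) |
|---|---|---|---|
| 64 | 0.20 | 0.071 | ±0.139 |
| 64 | 0.50 | 0.088 | ±0.173 |
| 80 | 0.20 | 0.063 | ±0.124 |
| 80 | 0.50 | 0.079 | ±0.155 |

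**3. Effect of an imbalance on the estimate.** Let large versus small fibroids change MMAS by b1 under LNG-IUS and b0 under TXA. An imbalance d, split evenly about the overall prevalence, shifts the arm difference by b1(d/2) − b0(−d/2) = d × (b1 + b0)/2. Only the size effect averaged over the arms matters. With d = 0.173 (64 per arm, p = 0.50, at the 95% limit):

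| Average size effect (assumed) | Shift | Share of 0.58 SD |
|---|---|---|
| 0.2 SD | 0.035 SD | 6% |
| 0.5 SD | 0.087 SD | 15% |
| 0.8 SD | 0.139 SD | 24% |

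If size matters only under LNG-IUS, by 0.5 SD, the average is 0.25 SD. The shift is 0.173 × 0.25 = 0.043 SD, about 7% of 0.58. If the two effects are equal and opposite, the shift is zero. For scale, the standard error of the comparison is sqrt(2/64) = 0.177 SD.

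**4. Is the test distorted?** Simulation with 64 per arm, 10,000 trials per scenario, residual SD 1 and a binary size factor. The assumed effects were a 0.5 SD interaction only, a 0.5 SD main effect only, or a 0.25 SD main effect with a 0.5 SD interaction.
- Type I error without adjustment: 4.7% to 5.0%.
- Mean unadjusted estimate for a true 0.58: 0.579 to 0.580.
- Power: 88.0% to 89.1% without size, and 89.4% to 90.2% with size as a main effect.

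Unadjusted power is a little below 90.2% here because the size variance is added to a residual SD of 1.

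**5. Gain from adjustment.** Take the planning SD as 1 and let size explain a share R² of the variance beyond baseline. The residual SD becomes sqrt(1 − R²), and the standardised effect becomes 0.58 / sqrt(1 − R²). The documents do not give R², so a range is shown.

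| R² (assumed) | Power at 64 per arm | n per arm for 90% |
|---|---|---|
| 0 | 90.2% | 64 |
| 1% | 90.5% | 63 |
| 5% | 91.6% | 61 |
| 10% | 92.9% | 58 |
| 20% | 95.4% | 51 |

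The case in step 3 where size acts only under LNG-IUS sits near the low end: 0.25² × 0.5 × 0.5 = 0.016, or roughly 1.5% of variance.

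**The case against.** The strongest reply is that nothing is broken. Randomisation makes the comparison unbiased, and the standard error already allows for chance imbalance in factors left out of the model. Step 4 bears this out. A reader might infer that imbalance in size passes straight into the primary result as an uncontrolled error. The documents and the arithmetic do not support that: even 0.087 SD, at the 95% limit with an assumed 0.5 SD effect, is about half of one standard error.

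A reader might also take size to be the protocol's main prognostic factor. Section 2 calls it a modifier of the contrast and lists it beside BMI; nothing says it predicts MMAS across arms. The background in 1.1 points the other way. It expects TXA to work better where fibroids are larger, while Section 2 expects LNG-IUS to do worse. Opposite effects cancel in the average, and with them most of the gain from a main-effect covariate.

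The ANCOVA already removes any size effect that runs through baseline MMAS. The size hypothesis is not ignored either: the Fine-Gray models can condition on size, so imbalance does not bias them.

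Lastly, three other balancing factors are a legitimate choice. Section 1.1 describes more than a year of enrolment and randomisation, so a fourth factor now would be a discretionary mid-trial change with little demonstrated benefit.

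All of this stands and limits the point to precision and pre-specification. It does not explain why a value already recorded, and predicted to matter, should stay out of the MMAS model. It also leaves the predicted modification untested on that score.

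**Conclusion.** The omission is confirmed in both places: size is neither a minimisation factor nor a term in an MMAS model. The consequence is a modest loss of efficiency, with no bias and no inflation of type I error. Over assumed R² of 1% to 10%, adjustment is worth about 0.3 to 2.7 points of power at 64 per arm, and about 5 points at 20%. It is worth close to nothing if size acts in opposite directions in the two arms. These figures rest on assumed values, because the documents give no association between size and MMAS and no distribution of size.

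The point concerns the randomised comparison only. It is a free improvement to the analysis plan and does not justify altering the allocation scheme.

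**What to change.** In 7.2, pre-specify baseline largest fibroid diameter, as a continuous variable, as a covariate in the 6-month MMAS ANCOVA alongside baseline MMAS. Add a secondary model with a size-by-arm term, because a main effect alone does not test the prediction "Large fibroid size will limit the effectiveness of LNG-IUS compared with TXA". Leave the allocation factors in 5.3 as they are.

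The cost is one degree of freedom for the main effect, one more for the interaction in the secondary model, and a few lines of SAP text. No increase in sample size is needed. There is one limit: under footnote 1 of Table 1, saline sonogram, ultrasound or MRI from the year before enrolment can stand in for the study scan. Diameters may therefore come from mixed modalities and be up to a year old, which may dilute the gain. The SAP should state which measurement is used when more than one exists.

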5.4 Preparation and Administration of Study Drug

Levonorgestrel intrauterine system (20microgram/24 hour levonorgestrel) will be sent from the manufacturer (Bayer Pharma AG) in sterile packaging to the clinic for insertion by physician as per clinical protocol. After pregnancy has been reliably excluded, the patient is placed in the lithotomy position and a bimanual examination is performed to assess uterine size and position. A speculum is placed in the vagina and the cervix cleaned with antiseptic solution. The uterus is sounded. The package is opened and using an aseptic technique, the sterile inserter is removed from the package. The slider is pushed forward as far as possible in the direction of the arrow to load the LNG-IUS. The inserter is carefully placed in the cervix and advanced to the uterine fundus corresponding to the sounding depth. The LNG-IUS arms are opened by pulling back the slider, the LNG-IUS positioned at the fundus, and the inserter removed. Strings should be cut to 3 cm.

Tranexamic acid will be dispensed by the Mayo Clinic Outpatient Research Pharmacy to the participant or mailed directly in 3-month supply increments. Participants will be instructed to take TXA at the initiation of each menses and use during the heaviest days of bleeding for up to 5 days. Dosage is 1.3 grams (2 pills of 650mg each) three times per day for up to 5 days.

5.5 Subject Compliance Monitoring

The study team will assess use of the medications at each follow-up phone call and visit. Subjects will be encouraged to feel for strings of the LNG-IUS to ensure uterine location. The TXA arm will be asked about the number of days they are using per menstrual cycle.

Prior and Concomitant Therapy

Concomitant therapy with NSAIDs will be allowed in both arms for treatment of dysmenorrhea or excessive bleeding. We will record NSAID use during the menstrual cycle. Estrogen-

containing medications are contradicted with TXA and thus, will not be allowed to be used during the study.

5.6 Packaging

Mirena (levonorgestrel-releasing intrauterine system), containing a total of 52 mg LNG, is available in a carton of one sterile unit NDC# 50419-423-01.

Mirena is supplied sterile. Mirena is sterilized with ethylene oxide. Do not re-sterilize. For single-use only. Do not use if the inner package is damaged or open. Insert before the end of the month shown on the label.

LYSTEDA (tranexamic acid) tablets are provided as white oval-shaped tablets. Each tablet is debossed with the marking “FP650” and are supplied as:

Quantity	Package Type	NDC Number
30 tablets	HDPE bottle	55566-2100-2
100 tablets	HDPE bottle	55566-2100-1

The TXA will be dispensed by the Research Pharmacy to study participants during their clinic visit or by mail. The investigational product will be labeled with patient specific prescription labels and the appropriate labels affixed to the prescription bottles/package as required by state and federal regulations.

The package of an investigational new drug intended for human use shall bear a label with the statement "Caution: New Drug--Limited by Federal (or United States) law to investigational use". A sample label is provided in the figure below. Note that the label is subject to change format but the information contained therein will not be changed.

Sample Label

MAYO CLINIC
 RESEARCH MEDICATION Today's Date:
 [name]
 [name] Prescriber Name/Number:
 [contact]

IRB# 16-008671 Subject # _____ Subject Name _____
 Study Name _____ Kit# _____
 Medication Name/Strength Mirena (levonorgestrel-releasing intrauterine system)
 Directions (NO Abbreviations) _____

Caution-New Drug Limited By Law To Investigational Use

Sample Label

MAYO CLINIC
 RESEARCH MEDICATION Today's Date:
 [name]
 [name] Prescriber Name/Number:
 [contact]

IRB# 16-008671 Subject # _____ Subject Name _____
 Study Name _____ Kit# _____
 Medication Name/Strength Tranexamic Acid 650mg
 Directions (NO Abbreviations) Two tablets three times per day for up to 5 days
 during the menses _____

Caution-New Drug Limited By Law To Investigational Use

5.7 Masking/Blinding of Study

Neither subjects nor researchers can be blinded to the treatment arm due to the nature of the study medications.

